9.5 Physical Assessments

Descriptive summaries of results heart rate and BSA as a result of physical assessments at the time of echocardiographs will be summarized with descriptive statistics by treatment group and time point.

A data listing will display all results from physical assessments.

10. EFFICACY ANALYSIS

Effectiveness endpoints are all secondary endpoints and are the New York Heart Association (NYHA) functional classification score and the echocardiographic hemodynamic measures of peak and mean gradient and effective orifice area (EOA).

Additional echocardiographic assessments including the indexed EOA, MOA by the pressure half-time method, performance index, cardiac output, cardiac index and amount and location of any valvular regurgitation will be included in the efficacy analyses.

All secondary endpoints and assessments will be summarized with descriptive statistics by treatment group and visit. Mitral valve subjects will also be stratified by location. To assess treatment group differences, quantitative endpoints will use a two-sample Z-test (or t-test for small samples), ordinal endpoints will use a Wilcoxon rank-sum test, and nominal endpoints will use the chi-square test of association.

All data will be included in data listings.

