- Enter the shipment information into the Clinipace database. In 24 hours the lab should respond that the sample has arrived properly. Hint: arrange the testing and shipment schedule to occur early in the work week to avoid any overnight sample arriving at the lab on the weekend.
- Randomize the patient 2 weeks prior to their 3 month visit and either order clopidogrel for test group patients or provide QAS with the study INR target range for the control group patients and the home test machine order. The clopidogrel prescription is for a 90 day supply with 7 refills the dosing regime is 300mg loading dose on day 1 and 75mg/day thereafter.

• Conduct the 3 month visit which will start the study for the patient. Change drug therapy per the protocol and randomization result.

Preoperative Procedures -

The investigator will determine and document on CRFs whether each patient meets the selection criteria previously outlined before enrollment into the study. He will also obtain informed consent for study participation from each patient prior to implantation of the study device. A copy of the informed consent form will be kept by the investigator in the patient's study notebook. Patients not meeting the selection criteria or not receiving informed consent **should not** be enrolled in the study.

The investigator will determine and record on CRF1 each patient's demographics and relevant medical history, i.e., age at implant, gender, New York Heart Association (NYHA) functional class, cardiac rhythm, disease etiology, previous cardiac surgery, relevant information to determine thromboembolic risk group and valve lesion (i.e., stenosis, regurgitation or mixed stenosis/regurgitation).

These instructions are made to assist the study coordinator in filling out the form. Complete all items on the form. If information is unavailable to answer any item, make a note on the form and attach an explanation, as appropriate. When asked to specify a particular answer, use a short description. Please check any and all items that apply to the patient.

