For patient study number, use a 6 digit code. The first two digits are your center number, as assigned by the sponsor. The third number represents the position of the implant; 1 for aortics, and 2 for mitrals. The last three digits are assigned sequentially to each patient. For example, if your center number is 99, your first aortic patient study number is 991001, your first mitral patient study number is 992001, and so forth. Once the patient study number is assigned on CRF1, use of the patient study number is required to identify the patient on subsequent forms.

NYHA functional class uses the nomenclature of that association. For the purposes of this study the commonly used classes of IIa and IIb are not used, either subgroup is considered class II.

Any failure to obtain prior informed consent must be reported to the sponsor, and the institution within 5 working days.

Previous cardiovascular surgery should be noted with a one or two word name of surgery and the date performed (page 2 of CRF1). Room is given for three prior procedures. Attach a separate explanation if more prior surgery was done. For coronary artery bypass surgery, please note the number of grafts by the following notation: CABG x 2 = double graft; CABG x 3 = triple graft; and so on.

If the patient has been maintained on any permanent or long-term preoperative Coumadin therapy, the preoperative INR should be measured and recorded within 72 hours prior to surgery. **Operative Procedures** -

The surgical technique employed is that developed and perfected by the principal investigator in his normal practice of cardiac surgery. Operative details such as cardioplegia are not specified in the protocol, but must be documented on CRF2.

The investigator will record on CRF2 information regarding the particular valve(s) implanted and other details concerning the surgery such as suture technique and any concomitant procedures. Carefully record the valve position, size and serial number.

Use the patient study number assigned on the preoperative form (CRF1) to identify the patient. Check any and all of the items that apply to this patient. Where explanations are needed, print a brief description of the required data.

For concomitant procedures, there are spaces for these additional procedures. Write in the name of the procedure done. For coronary artery bypass grafting, also note the number of grafts (i.e., CABG x 2 = double graft, CABG x 3 = triple graft, and so on).

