The rotatable sewing ring is made from polytetrafluoroethylene (PTFE) fabric attached to the valve housing by means of titanium retaining rings and 5-0 suture material. The

retaining rings positively attach the sewing ring to the valve housing by straddling a flange on the housing OD. They also provide the means for radiographic visualization and identification. There are no coatings or treatments on the fabric, although black orientation marks are included on the ring fabric. The sewing rings are supra-annular and allow the tissue annulus to abut the pyrolytic carbon housing directly, except in sizes larger than 25 mm, where the sewing rings become intra-annular to allow the 25 mm housing (largest size made) to fit properly into larger tissue annuli.

Valves are packaged on a valve holder with a separately packaged, removable handle to facilitate insertion and in situ orientation, and to provide protection during shipment and handling. The package is designed for shipment protection as well as handling ease. Valves are surgically clean and have been sterilized. The instructions for use packaged with the valve describe the handling of the valve during surgery in detail. Adhere to all instructions, warnings and precautions in the labeling.

A review of the literature on Coumadin anticoagulation of mechanical heart valve prostheses is inconclusive on the preferable therapy for various valves. Various groups have struggled with the lack of information on the subject of anticoagulation; yet have crafted recommendations based on information available. These include the ACCP⁽³⁾ and AHA/ACC⁽⁴⁾ recommendations. Butchart⁽⁵⁾ in a review of embolism in prosthetic heart valves concluded that valves vary in susceptibility to thrombosis due to subtle design differences, that optimal INR range is often uncertain, and that further research is needed.

Many studies of various mechanical valves have attempted to examine low intensity Coumadin therapy, Coumadin plus aspirin, aspirin alone and even no anticoagulation. These studies have had mixed results. Horstkotte ⁽⁶⁾ suggested that INR levels of 3.0 to 4.5 are too high for the St. Jude valve, but that a prospective trial is needed to show the proper level. Cannegieter ⁽⁷⁾ in the first detailed study of optimum anticoagulation suggested the target of 3.0 to 4.5 initially.

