6.2 Strata and Covariates

All primary and secondary analyses utilizing Kaplan-Meier life tables will be stratified by risk factors including age and gender. Additionally, MVR treatment groups will be stratified by continent (e.g. North America vs. Italy) for all primary and secondary endpoints.

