8.6 Operation Data

Aortic and Mitral valve size and cross clamp time will be summarized with descriptive statistics by treatment group. Treatment group differences will be assessed with a two-sample Z test for cross clamp time and with the chi-square test for valve size.

All operative data will be included in data listings to include the following: complete valve information, suture technique, cross clamp time, cardioplegia, and Intraoperative drugs.

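### Aortic gradients and effective orifice area are tested without adjustment for implanted valve size, which is already recorded before randomization

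*SAP*

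**What the plan says.** SAP section 10 lists peak gradient, mean gradient, EOA and NYHA class as the effectiveness endpoints, all secondary. Its rule for between-arm testing is that "quantitative endpoints will use a two-sample Z-test (or t-test for small samples), ordinal endpoints will use a Wilcoxon rank-sum test", with a chi-square test for nominal measures. The only stratifier it mentions is geographic and mitral: "Mitral valve subjects will also be stratified by location".

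SAP section 6.2 does not fill the gap. It says "All primary and secondary analyses utilizing Kaplan-Meier life tables will be stratified by risk factors including age and gender", which confines age and gender to the Kaplan-Meier analyses, and otherwise adds only continent for the mitral groups. Protocol III.H allows stratification by age and other suitable factors, but ties neither to these endpoints.

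Valve size is collected. Protocol III.C, Operative Procedures, instructs: "Carefully record the valve position, size and serial number" (on CRF 2), and CRF 6 has a field for it at each echo. The SAP uses it as a balance check in section 8.6: "Treatment group differences will be assessed with a two-sample Z test for cross clamp time and with the chi-square test for valve size". It also enters indirectly. Protocol Appendix F, item 4.1, takes geometric orifice area (GOA) from valve size, and SAP section 7.3 defines the performance index as EOA/GOA.

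NYHA class is collected preoperatively on CRF 1 (Protocol III.C, Preoperative Procedures: "age at implant, gender, New York Heart Association (NYHA) functional class") and again on CRF 3 at discharge or 30 days. SAP Tables 14.2.1.1 to 14.2.1.3 summarise pre-randomization class, but the planned test does not use it.

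**The concern.** Geometric orifice area is set by valve size, so EOA, and plausibly gradient, should vary with size whatever the arm. In a two-sample Z- or t-test that variation stays in the error term. A chance difference in size mix between arms would also shift the observed difference in gradient or EOA, and the planned test has no means of removing it. SAP section 8.6 would show such an imbalance but says nothing about what follows from it.

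What is at stake is the precision of secondary haemodynamic comparisons. No echo of the study valve is scheduled before randomization (Protocol III.D requires echoes at 1, 3 and 5 years), so a baseline gradient or EOA is not available as a covariate. Valve size is the obvious one that is.

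**Working it through.** **1. Is there a plan figure to reproduce?** Not for these endpoints: the documents state no standard deviation, effect size or power for gradients, EOA or NYHA class. The only sizing concerns the primary events. For one-sided alpha 0.05, 80% power, 7.3% versus 6.0% and margin 1.5%, Protocol Table 1 gives 992 patient-years. The unpooled formula gives (1.645 + 0.842)² × (0.073×0.927 + 0.060×0.940) / (0.015 + 0.013)² = 979, which is 1.3% lower and close enough. It has no bearing on the present point.

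**2. Is valve size a legitimate covariate?** It is fixed at implant. Protocol III.B and III.C place randomization at the 3-month visit, two weeks before it, or at the enrolment visit for mitral patients who enrol later than 3 months after surgery. Under every version size precedes allocation, so adjusting for it cannot introduce post-randomization bias.

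**3. Size of the gain.** Let R² be the share of within-arm variance explained by valve size (assumed; the documents give none). Then

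- adjusted SE / unadjusted SE = √(1 − R²)
- equivalent sample per group = n / (1 − R²)

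Take n = 200 per group (AVR high risk, Protocol II.D) and two-sided alpha 0.05 (SAP 6.5). The unadjusted SE is √(2/200) = 0.100 SD, so the difference detectable with 80% power is 0.100 × (1.960 + 0.842) = 0.280 SD. For that same difference:

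| Assumed R² | SE ratio | SE reduction | Equivalent n per group | Power (80% unadjusted) |
|---|---|---|---|---|
| 0.05 | 0.975 | 2.5% | 211 | 82% |
| 0.10 | 0.949 | 5.1% | 222 | 84% |
| 0.20 | 0.894 | 10.6% | 250 | 88% |
| 0.30 | 0.837 | 16.3% | 286 | 92% |
| 0.40 | 0.775 | 22.5% | 333 | 95% |
| 0.50 | 0.707 | 29.3% | 400 | 98% |

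Example at R² = 0.20: SE = 0.100 × 0.894 = 0.0894 SD, and power = Φ(0.280/0.0894 − 1.960) = Φ(1.17) = 88%.

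The percentage reductions do not depend on n. At 150 per group (AVR low risk) the detectable difference falls from 0.323 SD to 0.315 SD at R² = 0.05 and to 0.229 SD at R² = 0.50. Echo numbers at 3 and 5 years may be smaller than either figure.

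**4. NYHA class.** The formula above does not apply to a rank test, so this was simulated: 200 per group, 4,000 runs, a latent normal score cut into four classes, and an assumed shift of 0.3 SD. The ordinary Wilcoxon test was compared with the van Elteren test stratified by baseline class.

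| Assumed latent correlation, baseline with follow-up | Wilcoxon power | Van Elteren power |
|---|---|---|
| 0.3 | 68% | 70% |
| 0.5 | 69% | 77% |
| 0.6 | 69% | 80% |

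With no shift, both tests rejected in about 5% of runs.

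**The case against.** The strongest reply is that this is a preference and not an error. Under randomization the two-sample tests keep their type I error. The endpoints are secondary, with no margin, power target or success rule, and the decision criterion in SAP 2.3.1 is thromboembolism plus major bleeding. All of that stands, and it limits the point to efficiency.

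Second, valve size is partly handled. SAP 8.6 would reveal an imbalance, and the performance index compares a size-scaled EOA in the same section 10. This also stands, so a reader should not infer that every aortic haemodynamic comparison ignores size. But a balance test changes no estimate, and the gradients have no size-scaled counterpart. Indexed EOA divides by body surface area, not by valve size.

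Third, the magnitude is assumed. A reader might infer from R² of 0.20 to 0.50 that adjustment is worth 25% to 100% more echo studies (1/0.80 = 1.25; 1/0.50 = 2.00). The documents contain nothing that fixes R² in that range, so this cannot be stated as a result.

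Two further readings go beyond the text. One is that section 10 tests separately at every visit: it attaches visit to the descriptive summaries, while its testing sentence does not mention visit. The other is that 3-month NYHA class is a clean baseline. Protocol III.C has sites randomize two weeks before that visit, and mitral patients enrolling late are randomized at enrolment, so the 3-month value may follow allocation. Preoperative class may also relate only weakly to later class.

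**Conclusion.** The point holds as a free improvement. SAP section 10 leaves a recorded, pre-randomization and plausibly prognostic covariate out of the tests of aortic peak gradient, mean gradient and EOA. The standard error would fall by about 3% if size explains 5% of the variance and by 29% if it explains 50%. That range is an assumption, and the documents cannot narrow it. For EOA the case rests on the documents' own link between valve size and geometric orifice area. For gradients it rests on the same link by inference.

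The planned analysis is not invalid or biased under randomization, and nothing here touches the primary decision. Nor does the argument call for a joint model over the 1-, 3- and 5-year echoes. That is a separate choice with its own missing-data assumptions. For NYHA class the gain ranges from negligible to moderate (2 to 11 percentage points of power in the simulated settings), so that part is optional.

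**What to change.** In SAP section 10, for aortic peak gradient, mean gradient and EOA, replace the two-sample Z/t-test with a linear model (analysis of covariance) at each echo visit, containing arm and labelled valve size. Enter size as a categorical factor: Protocol section IV says that labelled sizes above 25 mm share the 25 mm housing, so a linear term would be misspecified there. State in advance how sparsely used sizes will be combined. Keep the unadjusted summaries as descriptive tables, and leave the mitral stratification by location as it is.

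Optionally, replace the NYHA rank-sum test with a van Elteren test stratified by the last class recorded before the randomization date. Where the 3-month visit follows randomization, that means the discharge/30-day or preoperative class.

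The cost is a few lines of SAP text and modest programming, with no new data. The change should be dated before echo results are compared by arm, so that the covariate is not chosen after seeing them.

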11. INTERIM ANALYSIS

No interim analyses are planned, but they may occur at the request of the Data Safety Monitoring Committee, or the request of the Principal Investigators and approval of the Sponsor as a result of their annual meeting, or the FDA.

12. END-OF-STUDY-ANALYSIS

A final analysis will be conducted after the last patient completes or discontinues the study and the resulting clinical database has been cleaned, quality checked, and locked.

